12.6. Secondary and Tertiary Efficacy Endpoints

Key secondary efficacy endpoints are also of interest for this study, in terms of controlling the overall Type I error rate. A gatekeeping or stepdown approach will be used to test the primary efficacy endpoint and then specific secondary efficacy endpoints sequentially in order to preserve the study-wise Type I error rate. The sequence for the stepdown procedure in this study is as follows:

1. Test the primary efficacy endpoint: percent change from baseline to Week 12 in LDL-C
2. Test the percent change from baseline to Week 24 in LDL-C
3. Test the percent change from baseline to Week 12 in non-HDL-C
4. Test the percent change from baseline to Week 12 in TC
5. Test the percent change from baseline to Week 12 in apoB
6. Test the percent change from baseline to Week 12 in hs-CRP

In this hierarchical testing structure, each hypothesis is tested at a significance level of 0.05, two-sided. Statistical significance at each step is required in order to test the next hypothesis. If the primary endpoint meets the criteria for statistical significance, then the percent change from baseline to Week 24 in LDL-C will be tested; and so forth.

In general, change or percent change in lipid parameters at a given time point will be analyzed using similar ANCOVA model for the primary endpoint with treatment group, CV risk (ASCVD only; HeFH with or without ASCVD) and baseline statin intensity (high intensity, moderate intensity, low intensity) as factors and the relevant baseline as a covariate.

Baseline for HDL-C, non-HDL-C, TG, and TC will be defined as the mean of the lipid values from Week -1 (Visit S3) and predose Day 1/Week 0 (Visit T1). If a repeat lipid measurement is performed at Week -1 (Visit S3), then baseline will be the mean of the lipid values from the second Week -1 assessment and predose Day 1/Week 0 (Visit T1). Baseline for apoB and hs-CRP will be defined as the predose Day 1/Week 0 (Visit T1) value.

Each ANCOVA will be performed using the FAS, with patients included in their randomized treatment group regardless of the treatment they actually received. Same imputation method described for the primary endpoint will be used for those secondary endpoints included in the step-down procedure, while only observed data analysis will be used for other secondary and tertiary endpoints. For each lipid parameter and analysis time point, the LSM and SE will be provided for both treatment groups, along with the placebo-corrected LSM, its 95% CI and associated p-value.

The ANCOVA assumption of normality will be assessed. If non-normality of the data is found at any time point for any parameter, either the data will be transformed so that it is normally distributed or a nonparametric test will be considered instead of the planned ANCOVA.

Percent change from baseline to Week 24 and to Week 52 LDL-C will be analyzed similarly with patients in the FAS who did not receive additional lipid-lowering therapy by that time point (by Week 24 for the Week 24 analysis; by Week 52 for the Week 52 analysis) included in the analyses. Only observed case data will be used (no imputation for missing data). Output from each time point will include the LSM and SE for each treatment group, as well as the placebo-correct LSM, 95% CI, and p-value.

12.7. Additional Post-randomization Adjunctive LDL-lowering or Triglyceride-Modifying Therapy

The number and percent of patients in each treatment group requiring additional (post-randomization) adjunctive LDL-C or triglyceride-modifying therapy will be summarized. Medications and the reasons for their additional treatment (hyperlipidemia vs. hypertriglyceridemia) will be summarized separately.

12.8. Safety Endpoints

The summarization of AEs will include TEAEs. TEAEs and SAEs will be summarized by SOC, severity, and relationship to study drug for each treatment group. These AE summaries will include cumulative incidence (percent of patients experiencing the AE) and patient-year adjusted incidence rates. If appropriate, absolute and relative risk differences will be calculated using both cumulative incidence and incidence rates. Deaths, withdrawal from study treatment due to AEs, and withdrawal from the study due to AEs will each be summarized by treatment group.

Clinical safety laboratories, including hematology, blood chemistry, coagulation, HbA_{1C}, glucose, and urinalysis; PE findings; vital signs; ECG readings; and weight will be summarized by the value and by change from baseline in the value (where appropriate) at each postbaseline time point.

Hepatic Safety

Liver-associated enzymes and TB will be summarized by the value and change from baseline in the value, by treatment group and visit. In addition, the number and percent of patients with abnormal values for ALT, AST, and TB will be summarized. These summaries of patients with abnormal values will be performed overall; by normal baseline; and by abnormal baseline for each of ALT, AST, and TB. Hy's law criteria ($\geq 3 \times$ ULN for either ALT or AST, with accompanying TB $> 2 \times$ ULN or patient's baseline) will also be applied to the data; any potential Hy's law cases will be listed separately. In the case of patients with Gilbert's disease, TB will be fractionated and the determination of $2 \times$ ULN based upon direct (conjugated) bilirubin. For patients with Gilbert's Disease $2 \times$ the conjugated bilirubin will be used as the criterion.

Musculoskeletal Safety

AEs of muscle-related symptoms will be summarized by treatment group. CK levels will be summarized by the value and change from baseline in the value, by treatment group and visit. In addition, the number and percent of patients with abnormal CK values will be summarized. These summaries of patients with abnormal CK will be performed overall; by normal baseline CK; and by abnormal baseline CK.

Diabetes and Hyperglycemia

Cases of new onset of diabetes will be recorded as AEs and will be summarized using the appropriate SOC. These events will be summarized by severity and relationship to study drug for each treatment group. Glucose and HbA_{1C} will be monitored at baseline and at Weeks 12, 24, and 52, and be summarized.

Renal Safety

Baseline eGFR will be summarized by treatment group for actual value and for baseline eGFR categories. Shift tables of eGFR category from baseline over the study, will be provided by treatment group. Shift tables of urine protein (negative/positive) from baseline over the study, will be provided by treatment group. Values of CK over the study will be summarized by treatment group and by baseline eGFR category. Finally, muscle-related AEs will be summarized by treatment group and by baseline eGFR category.

Neurocognitive Events

Neurocognitive events will be identified and evaluated by routine safety monitoring of PE findings and AEs. Summarization of neurocognitive events will occur using prespecified MedDRA terms and will be performed by SOC, severity, and relationship to study drug for each treatment group.

Clinical Endpoints

Clinical endpoints using standardized definitions will be adjudicated by an independent blinded expert CEC for all ongoing Phase 3 studies in the bempedoic acid program. Investigator-reported clinical endpoints and adjudicated clinical endpoints will be summarized by event type and treatment group. Additional details regarding the clinical endpoints and their definitions will be included in CEC Charter.

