5.2.4. Safety Endpoints

1. Patient incidence to TEAE
2. Safety laboratory values and vital signs
3. Cardiovascular event rates

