11.2.7. Treatment-Emergent Adverse Events

TEAE are defined as AEs that begin or worsen after the first dose of study drug.

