18.1. ADVERSE EVENTS

Adverse Events (AEs) will be coded using MedDRA, Version 20.1.

Treatment emergent adverse events (TEAEs) are defined as AEs that started or worsened in severity after the first dose of double-blind study medication and prior to the last date of study medication + 30 days. AEs that occurred on day 1 will be only be determined as TEAE if the site indicated it occurred after first dose on the AE CRF.

See [Appendix 2](#) for handling of partial dates for AEs. In the case where it is not possible to define an AE as treatment emergent or not, the AE will be classified by the worst case scenario, i.e. treatment emergent.

An overall summary of number of patients within each of the categories described in the sub-section below, will be provided as specified in the templates. Listings will include TEAEs and Non-TEAEs.

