18.1.1. ALL TEAEs

Incidence of TEAEs will be presented by System Organ Class (SOC) and Preferred Term (PT) and also broken down further by maximum severity and relationship to study medication. TEAEs will also be presented by PT in descending frequency. Adverse events by the subgroups in [Section 17.2.4](#) with the exception of baseline LDL subgroup will also be presented.

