18.1.4. TEAEs LEADING TO DISCONTINUATION OF STUDY MEDICATION

TEAEs leading to permanent discontinuation of study medication will be identified by using the

Statistical Analysis Plan

response of 'Drug Withdrawn/Permanently discontinued' on the Action Taken With Study Drug Field on the AE eCRF page. For TEAEs leading to discontinuation of study medication, summaries of incidence rates (frequencies and percentages) by SOC and PT will be prepared.

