18.3. CLINICAL ENDPOINTS

Clinical endpoints will be monitored and adjudicated by an independent blinded expert CEC for this study. The following clinical endpoints will be tabulated:

- CV death (MACE)
- Non-CV death (non-MACE)
- Nonfatal myocardial infarction [MI] (MACE)
- Nonfatal stroke (MACE)
- Hospitalization for unstable angina (MACE)
- Coronary revascularization (MACE)
- Non-coronary arterial revascularization (non-MACE)
- Hospitalization for heart failure (non-MACE)

Statistical Analysis Plan

Additional details regarding clinical endpoints and clinical endpoint definitions will be included in CEC charter. The number of patients with at least one adjudicated event and incidences and percentage of patients with each event will be presented in a table.

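### The protocol commits AE summaries to patient-year adjusted rates, but the SAP text specifies only counts and percentages, within a TEAE window that closes 30 days after last dose

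*Protocol*

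**What the plan says.** Protocol 12.8, repeated in the synopsis, states without condition that AE summaries will include "cumulative incidence (percent of patients experiencing the AE) and patient-year adjusted incidence rates". It adds that, where appropriate, "absolute and relative risk differences will be calculated using both cumulative incidence and incidence rates". Protocol 5.2.4 lists "Cardiovascular event rates" among the safety endpoints, with no denominator.

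The SAP text on AEs (18.1 to 18.1.6) presents TEAE incidence by system organ class and preferred term and mentions no patient-years. Where it does use the word rates, in 18.1.4, it explains them as counts and percentages: "summaries of incidence rates (frequencies and percentages) by SOC and PT will be prepared". For adjudicated events, 18.3 says that "incidences and percentage of patients with each event will be presented in a table".

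The two documents also define a TEAE differently. Protocol 11.2.7 has no end date: "TEAE are defined as AEs that begin or worsen after the first dose of study drug". SAP 18.1 counts only events that start or worsen "after the first dose of double-blind study medication and prior to the last date of study medication + 30 days"; later events appear only in listings. The SAP safety analysis set (5.1) is every randomized patient who took at least one double-blind dose. Exposure is derived in SAP 16.1 but summarized separately and never used as an AE denominator. Under Protocol 12.1 the SAP prevails where the two differ.

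**The concern.** Patients who stop the drug early are asked to stay on the visit schedule to Week 52 (Protocol 10.3.1), so planned follow-up is equal between arms. Countable time in the TEAE tables is not. A patient who stops at Week 6 contributes about 10 weeks to the numerator window (6 + 30/7 = 10.3) but a full unit to the denominator. If stopping differs between arms, the percentages compare unequal times at risk. The protocol's patient-year measure would adjust for this, and the SAP text omits it.

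Unequal stopping is plausible, but its direction cannot be predicted. The protocol ties withdrawal from study drug to liver enzyme, renal, hemoglobin and CK findings (11.1.6.3), and also to persistent LDL-C or triglyceride elevation (11.1.6.4), which could raise stopping on placebo. At stake is the reading of the 52-week safety comparison. That comparison is a stated objective (5.1.3), and Amendment 3 gives the size of the safety database as its reason for returning to 750 patients.

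**Working it through.** **No safety figure to reproduce.** The documents state no AE, cardiovascular or discontinuation rate. Their only computed design figure, more than 95% power for LDL-C with 500 against 250, reproduces (power about 1.000) but has no bearing here.

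**Inputs.** From the documents: 52 weeks of treatment (taken as 1 year), a window ending 30 days after last dose, and a denominator of all dosed patients. Assumed: a constant first-event hazard λ, stopping at a constant hazard so that a proportion D has stopped by one year, and events independent of stopping.

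**Formulas.** Let μ = −ln(1 − D) and g = 30/365 = 0.082.

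- Mean window in years = g + [1 − e^(−μ(1−g))]/μ
- Crude proportion = 1 − e^(−λg) + λe^(−λg) × [1 − e^(−(λ+μ)(1−g))]/(λ+μ)
- Patient-year rate = first events / time to first event or window end, which equals λ when the hazard is constant

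**Example, λ = 0.05 per year in both arms.**

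- D = 0.15: μ = 0.1625. Crude = 0.0041 + 0.0498 × 0.8339 = 4.56%; mean window 0.935 y.
- D = 0.25: μ = 0.2877. Crude = 0.0041 + 0.0498 × 0.7892 = 4.34%; mean window 0.889 y.
- Crude relative risk = 4.34/4.56 = 0.95; difference −0.22 points. The full 52-week risk is 4.88% in both arms, and the patient-year rate is 5.0 per 100 in both.

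**Range.** The placebo hazard is 5 per 100 patient-years; stopping is shown as placebo against the other arm.

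| Stopping | Crude RR, true ratio 1.0 | Crude RR, true ratio 1.3 | Rate ratio |
|---|---|---|---|
| 15% / 15% | 1.00 | 1.29 | 1.00 / 1.30 |
| 15% / 20% | 0.98 | 1.26 | 1.00 / 1.30 |
| 15% / 25% | 0.95 | 1.23 | 1.00 / 1.30 |
| 15% / 35% | 0.90 | 1.16 | 1.00 / 1.30 |
| 10% / 40% | 0.85 | 1.10 | 1.00 / 1.30 |

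With a true hazard ratio of 1.3, the full 52-week relative risk is 1.29. The result depends little on how common the event is: at 60 per 100 patient-years and a true ratio of 1.0, stopping of 15% against 25% gives 42.5% and 40.7%, a relative risk of 0.96.

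**The reverse case.** Suppose that all events occur soon after the first dose, with equal risk in the arms. The percentages are then correct, and the rate ratio is inflated by the inverse ratio of the windows: 0.935/0.889 = 1.05 for 15% against 25%, and 0.935/0.840 = 1.11 for 15% against 35%. Neither measure is safe alone.

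**The case against.** Several points on the other side are sound.

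- **The bias is conditional.** It needs unequal stopping and events that would have arisen after the window. Events that come early, or that themselves cause stopping, are counted in full. A reader might infer that the tables will understate risk on bempedoic acid; with no discontinuation figures and no predictable direction, the documents do not support that.
- **Cardiovascular events.** A reader might extend the argument to MACE. SAP 18.3 sets no 30-day limit for adjudicated events, and 18.2 covers deaths during the study. A treatment-emergent restriction appears only in a post-hoc table in the SAP addendum. Nor does the protocol promise patient-year cardiovascular rates: 5.2.4 gives no denominator, and 12.8 asks only for a summary by event type and arm. What remains is an undefined term.
- **The window has a basis.** Protocol 11.2.3 and 11.3 use 30 days after last dose for patient reporting of AEs and for SAE reporting. The limit is defensible for on-treatment events. It still differs from the TEAE definition in 11.2.7.
- **SAP silence is not revocation, and the table templates were not available.** SAP section 8 leaves table content to templates, which might include rates. The finding concerns the SAP text. That text gives its own meaning to incidence rates in 18.1.4, and it is not the protocol's.
- **Differences in exposure would be visible.** Exposure, treatment withdrawals and AE discontinuations are all summarized. A reader could see an imbalance but could not correct the AE tables for it.

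None of this answers the omission itself. The AE commitment in Protocol 12.8 is unconditional, and the SAP neither carries it out in its text nor explains the departure.

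**Conclusion.** The point holds as a gap between protocol and SAP on AE rates, with a conditional effect on the safety comparison. Under constant hazards and stopping spread over the year, a gap of 5 to 10 percentage points in stopping shifts the crude relative risk by about 2% to 5%, and a gap of 20 to 30 points by about 10% to 15%. The shift makes the arm that stops more look safer. With equal stopping there is no relative bias, although both percentages fall below the 52-week risk (4.56% against 4.88% in the example). These sizes rest on assumed hazards and discontinuation proportions. The finding does not show that the safety conclusions are wrong, and it does not establish a bias in the adjudicated cardiovascular or death summaries. It should be corrected because the protocol already specified the remedy.

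**What to change.** - **SAP 18.1:** beside the percentages for overall TEAEs, SAEs and AESIs, give patients with a first event per 100 patient-years by arm. Count time from first dose to first event, or to the earlier of last dose + 30 days and end of follow-up. If the sponsor prefers not to, state the reason for departing from Protocol 12.8.
- **SAP 18.3:** add events per 100 patient-years over all follow-up to last contact, so that the safety endpoint in Protocol 5.2.4 has a stated denominator.
- **SAEs:** add a summary of all recorded events to Week 52, because on-treatment rates do not remove informative stopping. Note that the reporting rule in Protocol 11.3 may leave later SAEs incompletely collected.
- **Definitions:** reconcile the TEAE definitions in Protocol 11.2.7 and SAP 18.1.

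The addendum says that the planned analyses are complete, so the AE rates would now enter at reporting, labelled as protocol-specified.

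The cost is modest. The dates are collected, but SAP 16.1 derives only first-to-last-dose exposure, so time to first event and to last contact must be programmed. The rates assume a roughly constant hazard and can make the arm that stops more look worse when AEs come early, which is why both measures should stay in the tables.

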12.9. Pharmacokinetics

Trough plasma concentrations of bempedoic acid and ESP15228 will be collected and summarized from patients prior to dose at Weeks 24 and 52 for use in further developing the population PK model.

13. DIRECT ACCESS TO SOURCE DATA/DOCUMENTS

13.1. Study Monitoring

The Sponsor (or its authorized representative) has the obligation to follow this study closely to ensure that the study is conducted in accordance with the protocol, International Conference on Harmonisation (ICH) and Good Clinical Practice (GCP) guidelines, national and international regulatory requirements, and the current Declaration of Helsinki throughout its duration by means of personal visits to the Investigator's facilities and other communications.

These visits will be conducted to evaluate the progress of the study, verify the rights and well-being of the patients are protected, and verify the reported clinical study data are accurate, complete, and verifiable from source documents. This includes review of ICDs, results of tests performed as a requirement for participation in this study, and any other medical records (eg, laboratory reports, clinic notes, study drug dispensing log, pharmacy records, patient sign-in sheets, patient-completed questionnaires, telephone logs, ECGs) required to confirm information contained in the eCRFs.

The monitoring strategy for the study foresees a risk-based monitoring approach, in line with the relevant Food and Drug Administration (FDA) and European Medicines Agency (EMA) recommendations, and will be described in details by the study-specific risk-based-monitoring plan.

A monitoring visit should include a review of the essential clinical study documents (regulatory documents, case report forms, medical records and source documents, drug disposition records, patient informed consent forms, etc) as well as discussion on the conduct of the study with the Investigator and staff.

The monitor should conduct these visits as frequently as appropriate for the clinical study. The Investigator and staff should be available during these visits for discussion of the conduct of the study as well as to facilitate the review of the clinical study records and resolve/document any discrepancies found during the visit.

All monitoring activities will be reported and archived. In addition, monitoring visits will be documented at the clinical site by signature and date on the study-specific monitoring log.

13.2. Audits and Inspections

Representatives of the Sponsor or its authorized clinical quality assurance group may visit a clinical site at any time during the study to conduct an audit of the study in compliance with regulatory guidelines and company policy. These audits will require access to all study records, including source documents, for inspection and comparison with the eCRFs. Patient privacy must be respected. The Investigator and clinical site personnel are responsible for being present and available for consultation during routinely scheduled site audit visits conducted by the Sponsor or its authorized representative.

The clinical study may also be inspected by the FDA or EMA (or other regulatory authority) to verify that the study was conducted in accordance with protocol requirements, as well as the applicable regulations and guidelines.

In the event the Investigator is contacted by regulatory authorities who wish to conduct an inspection of the clinical site, the Investigator will promptly notify the Sponsor of all such requests and will promptly forward a copy of all such inspection reports.

14. QUALITY CONTROL AND QUALITY ASSURANCE

To ensure compliance with GCP and all applicable regulatory requirements, the Sponsor / designee may conduct a quality assurance audit. Please see [Section 13.2](#) for more details regarding the audit process.

15. ETHICS

15.1. Institutional Review Board/Independent Ethics Committee Approval

Before initiation of the study, the Investigator must obtain approval or favorable opinion of the research protocol, ICD, and any material related to patient recruitment from an IRB or IEC. For locations participating within the US, the IRB must comply with the provisions specified in 21 Code of Federal Regulations (CFR) Part 56, ICH and GCP guidelines, and applicable pertinent state and federal requirements. For locations participating outside of the US, the IRB or IEC must comply with the applicable requirements of each participating location, including ICH and GCP guidelines, except where a waiver is applicable.

IRBs and IECs must be constituted according to the applicable laws. It is the responsibility of each clinical site to submit the protocol, IB, patient informed consent, patient recruitment materials (if applicable), and other documentation as required by the IRB or IEC for review and approval. A copy of the written approval must be provided to the Sponsor.

The documentation should clearly mention the approval/favorable opinion of the protocol, the patient informed consent form, and patient recruitment materials (if applicable), including respective version dates. The written approval and a list of the voting members, their titles or occupations, and their institutional affiliations must be obtained from the IRBs or IECs and provided to the Sponsor prior to the release of clinical study supplies to the clinical site and commencement of the study. If any member of the IRB or IEC has direct participation in this study, written notification regarding his or her abstinence from voting must also be obtained.

Clinical sites must adhere to all requirements stipulated by their respective IRB or IEC. This includes notification to the IRB or IEC regarding: protocol amendments, updates to the ICD, recruitment materials intended for viewing by patients, aggregate safety reports required by regulatory competent authorities, serious and unexpected AEs, reports and updates regarding the ongoing review of the study at intervals specified by the respective IRB or IEC, and submission of final study reports and summaries to the IRB or IEC.

It is the responsibility of each clinical site to submit information to the appropriate IRB or EC for annual review and annual re-approval.

The Investigator must promptly inform their IRB or IEC of all SAEs or other safety information reported from the patient or the Sponsor.

